#### **\*\*\* End Ame00163783 \*\*\***

For their appointment, participants will come to the Musculoskeletal Biomechanics and Imaging Laboratory located in the School of Kinesiology Building at the University of Michigan for one testing session lasting approximately 2 hours. All participants will be compensated for any parking expenses. Upon arrival, participants will be informed about the study procedures and have the opportunity to ask the research team questions before the start of the experiment.

Demographic data will be collected about the participant, including age, height and weight, and participants will complete a short questionnaire asking about their cancer diagnosis and treatment history. Participants will then be asked to change into a tank top. Baseline measurements of muscle stiffness and microvascular perfusion will be made with the participant sitting in a chair with the arm 90° abducted. Ultrasound shear wave elastography images will be obtained from 9 regions of the pectoralis major, one location on the serratus anterior and one location on the middle trapezius. Three images will be recorded from each location, resulting in 33 images. Ultrasound Doppler images will be obtained as a video clip as the muscle is swept top to bottom with the ultrasound transducer. The length of this video clip will vary but will be no longer than 90 seconds long and much shorter (<30 seconds) for most.

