After baseline measurements are completed, participants will be taken to the massage room where they will meet the massage therapist. Participants will be asked to remove all upper body clothing before lying down face up on the massage bed. They will be asked to cover their bodies, including chest and shoulders, with a sheet and woolen blanket. The massage therapist will leave the room while the participants get ready. Once the participant is ready, the massage therapist will re-enter the room and begin the myofascial massage. The treatment will last 30 minutes and focus on the chest and shoulder of the side that received the cancer treatment. Techniques applied during the intervention will include skin glide (variable time), stroking (2-3 minutes), scar tissue rolling (2-3 minutes), strumming (2-3 minutes), fascial stretch (3-5 minutes), circular friction (1-2 minutes), deep fascial release (3-5 minutes) and arm pull (60 seconds). The timing and order of each element will be varied based on tissue response and patient feedback. The massage therapist will carefully expose areas of the chest and/or shoulder to perform the treatment. A massage oil may be applied to the participant's skin if necessary. After the conclusion of the massage treatment, the massage therapist will leave the room so that the participant can get dressed again. No research personnel will be present in the massage room during the entire time.

Immediately afterward, participants will return to the examination room, where the measurements conducted at baseline will be repeated. Participants will then remain in the clinical suite (or an adjacent waiting room) for 60 minutes, after which all measurements will be repeated a second time. During their 60-minute wait period, participants will be asked to fill in the treatment satisfaction questionnaire. Additionally, participants will be allowed to keep themselves occupied (e.g., reading), and they will be allowed to use the TV entertainment system provided in the examination room.

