Participants will be randomized into two groups. One group will receive the massage treatment while the massage therapist will be permitted to more readily communicate with the participant, and one group will receive the same massage treatment while the massage therapist will restrict communication with the participant to only essential exchanges. When communication is permitted, the therapist will have a short consultation with the participant, explaining the massage techniques used and asking for specific areas of shoulder/chest discomfort/pain to focus the treatment on. During the treatment, the therapist and the participant will be allowed to converse freely. The therapist will ask for feedback regarding the massage technique applied and will adjust the technique (duration, intensity) accordingly. When communication is restricted, the massage therapist will only provide essential information about the treatment (how to get ready, when treatment will start and finish) to the participant. The participant will not be instructed to limit conversation (e.g. to alert the therapist if the intensity is too much), but the therapist will limit their responses.

We will withhold information about grouping and randomization from the participants until they complete the study visit to avoid a possible confounding effect of having this knowledge. We do not expect any adverse effects from withholding this information from the participants as all participants will receive the same standardized massage treatment. All participants will be handed a sealed envelope after the study which includes a letter informing them of the restricted/unrestricted communication component of the research study as well as the group for which they had been assigned.

Randomization will be done using covariate adaptive randomization controlling for the covariates of age and body mass index. A study coordinator will randomize participants and print each participant's group membership on a piece of paper, which will be placed in a sealed envelope. The envelope will be given to the massage therapist before meeting with the participant. Only the study coordinator and the massage therapist will have knowledge of each participant's group membership. All other research personnel involved in data collection (including those actively collecting ultrasound images) and analysis will be blinded to group membership until data analysis is complete for all participants.

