**AME00156146:**

We are required by the study funder (NCCIH) to screen for adverse events after the intervention. An adverse event questionnaire has been added to Section 29 of the IRB application to help our team identify adverse events (AE) and severe adverse events (SAE). This screener will be performed 7 – 10 days following the intervention. This can be delivered digitally, with a follow-up phone call if our team requires additional information from the participant or if the participant is unresponsive. Pain assessments taken at intake will also be reassessed during the screener.

The PI will maintain an adverse event log to grade the severity, study intervention relationship, action taken regarding study participation, outcome of the AE, expectedness, and SAE grading, along with the participant ID# and investigators initials and date of logging.

The potential risks of this project are anticipated to be no more than minimal risk with essential safeguards to protect the welfare of study participants. Only Adverse Events related to the study procedures (e.g., ultrasound imaging, myofascial massage) will be assessed for grade/attribution and recorded in the study database. These adverse events will be reported in aggregate form in conjunction with the completion of an annual continuing review application with the University of Michigan IRB board.

\*\*\* Begin **Ame00163783** \*\*\*

The potential risks of this project are anticipated to be no more than minimal risk with essential safeguards to protect the welfare of study participants. Only Adverse Events related to the study procedures (e.g., ultrasound imaging, myofascial massage) will be assessed for grade/attribution and recorded in the study database. These adverse events will be reported per the standard IRB-HSBS reporting guidance.

\*\*\* End **Ame00163783** \*\*\*

Per current institutional guidelines, the research team must report any serious adverse events resulting in death, life-threatening outcomes, hospitalization, or significant disability/permanent damage to the local IRB within seven calendar days of becoming aware of the event. Serious adverse events unrelated to the study procedures will be reported in aggregate form in conjunction with the completion of an annual continuing review application.

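### Does disclosing the group at the end of the visit undermine the pain and adverse-event reports collected 7–10 days later?

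*Combined protocol and SAP*

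**What the plan says.** The Experimental Design text in section 4 of the combined protocol and SAP sets the masking of participants in two sentences. The first is "We will withhold information about grouping and randomization from the participants until they complete the study visit", and the reason given is to avoid confounding by that knowledge. The second is "All participants will be handed a sealed envelope after the study which includes a letter informing them of the restricted/unrestricted communication component", and the letter also names the participant's own group. The same section brings participants to the laboratory "for one testing session lasting approximately 2 hours". The satisfaction score is taken inside that session: "During their 60-minute wait period, participants will be asked to fill in the treatment satisfaction questionnaire". On staff, it says "Only the study coordinator and the massage therapist will have knowledge of each participant's group membership"; everyone else who collects or analyses data stays blinded until the analysis is finished for all participants.

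The text of amendment AME00156146, placed after the endpoint table in section 6, adds an adverse-event screener 7–10 days after the massage because the funder requires one. It says "Pain assessments taken at intake will also be reassessed during the screener". The screener may be sent digitally, "with a follow-up phone call if our team requires additional information from the participant or if the participant is unresponsive". The amendment does not mention the group letter.

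**The concern.** With one visit and no follow-up, the end of the visit and the end of the study were the same moment, so the two disclosure sentences agreed. The amendment put 7–10 days between them and left the sentences as they were. The more natural reading is that the letter is given at the end of the visit. The first sentence points that way, and an envelope handed over in person needs a meeting, which a digital or telephone screener does not provide. A participant could then learn that communication was the experimental factor, and which arm she was in, about a week before she rates her pain and reports adverse events.

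Two things seem to be at stake. Pain defines eligibility, yet no pain score is described during the visit, so the screener supplies the only post-massage pain data in the documents. Self-reported pain is open to influence from knowing one's group. In addition, a participant who has read her letter and is then telephoned could tell her arm to someone who is meant to stay blinded.

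**Working it through.** No formula applies, and the plan gives no figure on this point. The sample-size statement in section 5 concerns shear wave velocity and is unaffected. The check is to put each data item in time order against the earliest possible disclosure, and then ask whether the plan uses that item to compare arms.

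**Earliest disclosure:** the end of the visit on day 0, from the two sentences in section 4.

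| Item | When collected | Listed endpoint in section 6? | Could follow disclosure? |
|---|---|---|---|
| Stiffness change, pectoralis major | Before, immediately after and 60 minutes after massage, day 0 | Yes (primary) | No |
| Perfusion change | Same three times, day 0 | Yes (secondary 1) | No |
| Stiffness change compared between groups | Same three times, day 0 | Yes (secondary 2) | No |
| Satisfaction questionnaire | During the 60-minute wait, day 0 | Yes (secondary 3) | No |
| Repeated intake pain items | Days 7–10 | No | Yes |
| Adverse-event screener | Days 7–10 | No | Yes |

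**Endpoints exposed through participant knowledge:** 0 of 1 + 3 = 4. **Self-report items exposed:** 2, neither of them an endpoint.

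**Planned use of those two items.** Section 5 names a repeated-measures ANOVA for shear wave velocity and color pixel density and a t-test for satisfaction. It names no test or summary of follow-up pain or adverse events by arm. Under AME00156146, as revised by Ame00163783, procedure-related adverse events are graded, logged and reported to the IRB. Pain is repeated as part of a safety contact and is not made an outcome.

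**Participants exposed.** If the end of the study includes the screener, 0 of 30. If the letter is given and read at the end of the visit, at most 30 of 30, with 7–10 days between disclosure and report. This range spans every possible value, so it bounds the exposure without measuring any bias.

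**What the letter adds.** By the end of the visit each woman has had 30 minutes of either free conversation or limited replies. The letter adds that a comparison exists and which side of it she was on. The adverse events to be recorded are those related to study procedures such as imaging and massage, which both arms receive.

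**The telephone route.** For this to reach an endpoint, four things must coincide: the call is triggered, the caller is blinded, the caller also handles image data, and the participant volunteers her arm. Her images have already been acquired by then, so only their processing could be influenced. The caller is not named and could be the study coordinator, who already knows the allocation.

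**The case for a change.** The strongest opposing case uses the protocol's own standard. It withholds the grouping because that knowledge could confound responses, and then adds subjective responses without saying whether the same protection covers them. The disclosure sentences would need only a short edit, the letter could be sent remotely, and the protocol itself expects no harm from withholding the information. The edit would leave the only post-massage pain data free of this weakness if they were ever compared by arm.

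The textual part of this stands: the order of letter and screener is not stated, and the amendment should ideally have settled it. What does not follow is that a planned result suffers. Ending participant masking once every endpoint has been collected is a coherent choice, and telling participants promptly about withheld information has value of its own. A later letter would delay that debriefing by about 7–10 days for every participant, to protect a comparison nobody has proposed.

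The staff arguments are weaker. "The PI will maintain an adverse event log to grade the severity, study intervention relationship", but no mechanism is apparent by which the participant's letter would alter that grading. Moving the letter would not stop a participant describing her session on the telephone. Nor would it stop her describing it to imaging staff during the visit, before two rounds of post-massage measurement, which is the more direct threat to blinding.

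**Conclusion.** The concern identifies a real gap in wording, but no change to the plan follows. Followed as written, under either reading of the disclosure point, the plan leaves all four endpoints and every planned analysis unaffected by what participants learn from the letter. The possible exposure is confined to two follow-up self-report items with no planned comparison by arm. It affects between 0 and 30 of 30 participants, and the documents give no basis for sizing a bias.

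This rests on three assumptions: the letter is not given before the last measurement of the visit, follow-up pain remains outside the endpoints, and adverse events are used for safety reporting and not to compare arms. If follow-up pain were later described by arm, a sentence saying that participants may have known their group would be enough. If the protocol is amended for some other reason, the order of letter and screener could be stated then as a clarification, but no conclusion of the trial depends on it.

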## STUDY SYNOPSIS

Title	Effects of myofascial massage and patient-therapist communication on shoulder muscle properties in breast cancer survivors with myofascial pain
Methodology	Longitudinal
Study Duration	1 year
Study Location	School of Kinesiology Building, University of Michigan
Objectives	To assess how myofascial massage and patient-therapist interaction alter the stiffness and microvascular perfusion of shoulder muscles
Number of Subjects	30 participants
Inclusion Criteria	
 
Female sex
 
Age 18 years or older
 
Previous unilateral breast cancer diagnosis
 
Treatment for primary breast cancer was completed 3 months to 2 years prior to enrollment (defined as completion of all treatments except oral maintenance therapies)
 
Myofascial pain in upper quadrant of the chest
 
Ability to understand and willingness to sign a written informed consent.
 

Exclusion Criteria	
 
Chronic neuromuscular or orthopedic injury currently affecting upper extremity function that is unrelated to their cancer diagnosis
 
Currently undergoing physical therapy, occupational therapy or other treatment for side effects related to their cancer diagnosis or other injury to the upper extremity
 
History of fibromyalgia
 
Broken or bruised skin in the chest/shoulder area
 
Diagnosed with metastatic breast cancer
 
Currently receiving treatment for other forms of cancer
 

Study Product(s)	Participants will be randomized 1:1 to receive one 30-minute myofascial massage either with patient-therapist communication permitted or restricted. Stiffness and microvascular perfusion of shoulder muscles will be measured non-invasively before the intervention, immediately afterward, and 60 minutes afterward. Muscle stiffness will be measured using ultrasound shear wave elastography, and microvascular perfusion will be measured with ultrasound-Doppler techniques. Participants will complete a questionnaire to assess the satisfaction with their treatment.
Statistical Methodology	A repeated-measures analysis of variance will be used to compare muscle stiffness and microvascular perfusion between intervention groups and their interaction. A two-sided independent t-test will be used to test for differences in treatment satisfaction between the groups.

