## 1) Study Objectives:

The objective of the proposed study is to assess how myofascial massage alters stiffness and microvascular perfusion of shoulder muscles and how these changes are influenced by patient-therapist communication. Specifically, we will examine superficial shoulder muscles in breast cancer survivors before and after they receive one session of myofascial massage. Participants will be randomized 1:1 to receive massage where communication with the massage therapist is permitted or restricted. Our primary hypothesis is that stiffness of shoulder muscles will be decreased, and microvascular perfusion will be increased after a 30-minute myofascial massage, and that the addition of patient-therapist communication will result in greater changes than massage alone with patient-therapist communication restricted. Our secondary hypothesis is that treatment satisfaction will be higher when communication is permitted compared to when communication is restricted.

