There are some potential risks to this experiment. There may be some discomfort from the ultrasound transducer indenting the skin. We expect the risk probability of this to be infrequent and the risk severity to be minor. To mitigate this risk, researchers will inform the participant prior to applying the transducer to skin and consistently ask participant if they are comfortable. There is also a small risk of an allergic reaction to the massage oil, if applied. We will minimize this risk by only using massage oil if necessary and asking the participants about known allergies before doing so. If an allergy may exist, we will not use massage oil. Finally, there is a minor risk of soreness and discomfort in the massaged regions which will subside within two days of treatment.

Loss of confidentiality is expected to be rare but is of major seriousness. To minimize the risk of loss of confidentiality, only authorized research personnel will have access to the data. Coded identifiers will be used, with a list housed within a locked cabinet inside of a secure office. This list includes name, subject ID, height, weight, and ethnicity as this information may be necessary covariates to include within our data analysis. PHI will not be written on paperwork and will be saved on separate from devices where research data is collected and stored. Paperwork will be shredded, and devices will be permanently destroyed or securely wiped 12 months after study completion.

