## 5) Statistical Design:

The objective of this study is to assess muscle stiffness and microvascular perfusion before and after a 30-minute myofascial massage and to investigate the additional effect of patient-therapist communication. Our primary hypothesis (H1) is that muscle stiffness will be decreased and microvascular perfusion will be increased and that these effects will be enhanced when patient-therapist communication is permitted. We will test this hypothesis with a repeated-measures ANOVA. The outcome variables will be shear wave velocity as representative measure of muscle stiffness and color pixel density indicating microvascular blood flow. Time (before, immediately after, and 60 minutes after massage) will be the within-subjects factor, and communication (permitted or restricted) will be the between-subjects factor. Interaction between time and type of communication will also be assessed. Our secondary hypothesis (H2) is that scores on the Global Satisfaction with Treatment questionnaire will be higher when patient-therapist communication is permitted during the massage treatment compared to communication restricted. We will test this hypothesis with a two-sided independent t-test.

The proposed study is a pilot investigation with shear wave velocity of the pectoralis major as primary outcome. Changes in shear wave velocity after myofascial massage have not been investigated previously. Thus, a formal power analysis was not completed. We estimate that if a moderate-to-large effect size is observed ( $f = 0.25-0.4$ ), our analysis plan can detect a significant within-between interaction (e.g., time by type of communication) with 8-18 participants (assuming alpha = 0.05, power = 80%, 2 groups, 3 repeated measures and correlation = 0.7). Accounting for data loss and study dropouts, we request to recruit 30 participants to complete this work.

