## 6) Objectives and Endpoints:

OBJECTIVES	ENDPOINTS	JUSTIFICATION FOR ENDPOINTS
Primary		

OBJECTIVES	ENDPOINTS	JUSTIFICATION FOR ENDPOINTS
1. To quantify changes in muscle stiffness in response to myofascial massage.	Change in muscle stiffness of the pectoralis major will be assessed by ultrasound shear wave elastography before and after myofascial massage	Muscle stiffness is hypothesized to decrease after myofascial massage is completed compared to baseline.
Secondary		
1. To quantify changes in muscle perfusion in response to myofascial massage.	Change in muscle perfusion of the pectoralis major and upper trapezius will be assessed by Doppler imaging and superb microvascular imaging before and after myofascial massage	Perfusion to muscle tissue undergoing massage is hypothesized to increase after myofascial massage is complete compared to baseline.
2. To evaluate the effect of patient-therapist communication on changes in muscle stiffness in response to myofascial massage.	Change in muscle stiffness of the pectoralis major will be assessed by ultrasound shear wave elastography and compared between patients randomized to a group with restricted or unrestricted communication with the massage therapist.	Effects of myofascial massage on muscle stiffness is hypothesized to be enhanced in patients without restricted communication with their massage therapist.
3. To evaluate the effect of patient-therapist communication on satisfaction with treatment	Responses to the Global Satisfaction with Treatment questionnaire will be compared between patients randomized to a group with restricted or unrestricted communication with the massage therapist.	Satisfaction with treatment is hypothesized to be enhanced in patients without restricted communication with their massage therapist.

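### Arms are balanced on age and BMI, but satisfaction is compared by an unadjusted t-test, which stays valid but is conservative and forgoes precision if either covariate predicts the score

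*Combined protocol and SAP*

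**What the plan says.** Section 4, under Experimental Design, sets the allocation: "Randomization will be done using covariate adaptive randomization controlling for the covariates of age and body mass index". The algorithm, any cut-points and the degree of randomness are not described. Section 1 gives the ratio: "Participants will be randomized 1:1 to receive massage where communication with the massage therapist is permitted or restricted".

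Satisfaction is secondary objective 3 in Section 6: "Responses to the Global Satisfaction with Treatment questionnaire will be compared between patients randomized to a group with restricted or unrestricted communication". For that hypothesis (H2), Section 5 says: "We will test this hypothesis with a two-sided independent t-test". The synopsis agrees: "A two-sided independent t-test will be used to test for differences in treatment satisfaction between the groups". Neither place names a covariate, and no other analysis in the document adjusts for age or BMI.

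**The concern.** Balancing the arms on a covariate largely removes its contribution from the difference in arm means. An unadjusted t-test still counts that covariate's variance as error. If age or BMI predicts the satisfaction score, the standard error is then too large for the design: the p-value and confidence interval are conservative, and precision that the allocation has made available is not used.

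What is at stake is the sharpness of one secondary comparison. With about 15 per arm the t-test can detect only large differences, so unused precision has some value.

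**Working it through.** **The plan's own figure.** Section 5 gives sample sizes only for the time-by-communication interaction: 8 to 18 participants for f = 0.4 down to 0.25, "assuming alpha = 0.05, power = 80%, 2 groups, 3 repeated measures and correlation = 0.7". With λ = f²·N·m/(1−ρ), df1 = (k−1)(m−1) = 2 and df2 = (N−k)(m−1):
- f = 0.4, N = 8: λ = 0.16·8·3/0.3 = 12.8, df2 = 12, power 0.810 (N = 6 gives 0.622).
- f = 0.25, N = 18: λ = 0.0625·18·3/0.3 = 11.25, df2 = 32, power 0.825 (N = 16 gives 0.769).

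The range reproduces. It says nothing about satisfaction, for which no power figure is given.

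**The planned t-test.** With 15 per arm, df = 28, the critical value is 2.05 and the noncentrality is d·√(15/2) = 2.74·d. Power is 80% at d = 1.06 (noncentrality 2.90) and 56% at d = 0.8 (2.19).

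**Why it becomes conservative.** Under perfect balance, the variance of the difference in means falls by the factor (1−R2), while the t-test still estimates the full variance. A large-sample limit for its type I error is 2·[1−Φ(1.96/√(1−R2))]. At R2 = 0.1 this is 2·[1−Φ(2.07)] ≈ 3.9%; at R2 = 0.3 it is 2·[1−Φ(2.34)] ≈ 1.9%. Real schemes balance imperfectly and should fall between this limit and 5%.

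**Simulation.** Assumptions, none given in the documents:
- N = 30, with a normal score of within-arm SD 1.
- Age and BMI independent and normal, with linear effects sharing R2 equally.
- Minimisation on thirds with a 0.9 biased coin (first figure), or on medians with a 0.8 coin (second figure).
- 40,000 trials per setting; Monte Carlo SE about 0.1 points for type I error and 0.2 for power.

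| R2 | Type I error, unadjusted | Power at 1.06 SD, unadjusted to adjusted |
|---|---|---|
| 0 | 5.1% / 5.1% | 79.8 to 78.4% / 80.3 to 78.5% |
| 0.1 | 4.2% / 4.3% | 80.9 to 83.1% / 80.5 to 82.4% |
| 0.2 | 3.5% / 3.7% | 81.2 to 86.9% / 81.3 to 86.7% |
| 0.3 | 3.0% / 3.3% | 82.0 to 90.8% / 81.6 to 90.6% |

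Adjusted type I error was 4.8 to 5.1% throughout. Separate simulations of the same two schemes put the unadjusted figure at 4.2 to 4.4% for R2 = 0.1 and 2.6 to 3.3% for R2 = 0.3. The algorithm matters somewhat: minimising on the continuous values (0.8 coin) gave 4.0% and 2.4%, and another median-split version gave 4.5% and 3.5%. Under plain 15:15 randomisation the t-test stayed at 4.9 to 5.1% for every R2 up to 0.5, so the conservatism comes from ignoring the balancing covariates.

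**Break-even.** At 1.06 SD, adjusting changes power by -0.6 / -0.7 points at R2 = 0.02 and +0.6 / +0.1 at 0.05, so the two analyses tie near R2 = 0.04 to 0.05. At 0.8 SD the changes are -1.3 / -1.8 points at R2 = 0, +3.1 / +2.5 at 0.1 and +13.5 / +13.1 at 0.3.

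**Unadjusted power as R2 rises.** Balance narrows the spread of the t statistic around its mean. This raises power when 2.74·d exceeds 2.05 (d above about 0.75) and lowers it below that. From R2 = 0 to 0.3, unadjusted power is therefore about flat at 0.8 SD and slightly higher at 1.06 SD. It falls from about 26% to 23-24% at 0.5 SD, and from about 12.5% to 9-10% at 0.3 SD.

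**Interval width.** Relative to the unadjusted interval, the adjusted one is 1.5 / 2.0% wider at R2 = 0, 3.9 / 3.3% narrower at 0.1 and 15 / 15% narrower at 0.3. This fits √0.9 = 0.95 and √0.7 = 0.84, less the small cost of estimating two slopes.

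**Repeated-measures ANOVA.** A covariate that shifts only a participant's level cancels from within-person contrasts. The primary before/after stiffness comparison and the time-by-communication test are then untouched. The interaction would be affected only if age or BMI predicted change over time, and the documents give no evidence of that.

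**The case against.** The best defence is that the planned test is valid and simple, the outcome is secondary, and the study is a pilot with no power claim for satisfaction. Nothing in the documents suggests that age or BMI predicts satisfaction with a single massage. They do not say why these covariates were chosen, and the choice may have been made for the ultrasound outcomes. Below break-even, adjusting is a tie or a small loss, and the notable gains need R2 near 0.3. All of this stands, and it is why the point is conditional and of low priority.

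The simulation is also idealised. The questionnaire's scale is not given, and Section 5 expects some data loss. With an illustrative five-level score with a ceiling (thirds, 0.9 coin), the gains shrink to 1.6-2.1 points at a latent R2 of 0.1 and 8-9 at 0.3. The direction holds.

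One might answer that covariates are already foreseen, because the confidentiality text in Section 4 says: "This list includes name, subject ID, height, weight, and ethnicity as this information may be necessary covariates to include within our data analysis". That sentence describes what the linking list contains. It is tentative and tied to no test, so it does not specify an adjustment. Equally, age being absent from it is not evidence about the model, and it needs no edit.

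A reader might infer from the allocation mismatch that the t-test is invalid or produces too many false positives. The error runs the other way. A reader might also infer that conservatism is harmless because unadjusted power never drops below its R2 = 0 level. That is true for large differences only, and the documents give no satisfaction effect size that would exclude small ones.

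**Conclusion.** The point holds as a conditional, low-priority improvement at medium confidence. The design balances on age and BMI, and the satisfaction analysis does not use them. If they are not prognostic, nothing is lost by the present plan, and adjusting would cost 1 to 2 points of power. If they explain 10% of score variance, adjusting gains about 2 points at 1.06 SD; at 30% it gains about 9 (13 at 0.8 SD). These sizes rest on assumed R2, algorithm, effect size and a normal score.

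It would be tempting to extend this to the primary stiffness endpoint or to call for covariates in the ANOVA. The documents do not support that. The communication main effect, which averages in the pre-massage value, corresponds to no objective in Section 6.

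**What to change.** In Section 5 and the synopsis, make the satisfaction analysis a linear regression of score on arm, age and BMI, both continuous, with arm tested two-sided at 0.05. Report the unadjusted t-test as a sensitivity analysis. Leave the repeated-measures ANOVA as planned; no covariate-by-time analysis is needed.

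The cost is one sentence in each place and two residual degrees of freedom (28 to 26 at N = 30), plus the small power loss already stated if neither covariate matters. No new data are needed: "Demographic data will be collected about the participant, including age, height and weight". Naming the model in advance also settles, before results are seen, which comparison is the main one.
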